| Methodology | 
• A pragmatic, multicentre, cluster-randomised, crossover, superiority trial with a primary endpoint of hip dislocation within one year integrated with Registry data collection.• In addition to usual registry data, the outcome will be determined by data linkage between the AOANJRR and hospital level data acquired through state governments or the Australian Institute for Health and Welfare. |
|-------------|---|

1. Introduction

1.1 About the AOANJRR

The AOANJRR was established in 1999 to improve outcomes for patients undergoing joint replacement surgery in Australia. The AOANJRR is federally funded and operates as a Federal Quality Assurance Activity. It has almost complete data on all hip and knee replacement procedures performed since it achieved full national implementation in mid-2002 (with over 1.5 million procedures now captured). In 2004 the AOANJRR extended to collecting all other joint replacements including shoulders, elbows, wrists, ankles and spines and full national data collection was implemented by 2008. Using revision, reason for revision and death as its principal end points, it has identified best practice with respect to prostheses choice, surgical technique, and patient selection. Making this information available to relevant stakeholders, including surgeons, has reduced post-operative complications and subsequent revision surgery.

1.2 Background

Hip fracture is the most serious and costly fall-related injury suffered by older people, affecting more than 25,000 Australians each year at a cost of more than \$1 billion in 2018.¹ Despite a reduction in the age-specific incidence of hip fractures secondary to effective preventive measures, the absolute number of hip fractures is increasing in Australia due to population growth and ageing.² Elderly patients with hip fracture are likely to experience significant functional impairment, decreased mobility and reduced quality of life that may necessitate the transition from independent living to a residential aged care facility.³ The one-year mortality following a fractured neck of femur is approximately 25%,⁴⁻⁶ and is associated with an increased risk of death that persists for several years after injury.⁷ International treatment guidelines therefore focus on reducing morbidity and mortality, as well as maximising functional independence post-fracture.

Nearly half of hip fractures are in the 'subcapital' (femoral neck) region, of which the majority are displaced.¹ These fractures are normally treated with arthroplasty, which involves either partial or complete replacement of the hip joint with a prosthesis. Traditionally, subcapital fractures have been treated with *hemiarthroplasty* (HA), which involves replacing the femoral head only, leaving the patient's acetabulum (socket) intact. An alternative form of arthroplasty is total hip arthroplasty (THA) which involves replacing the femoral head and the acetabulum (socket). Recent research has demonstrated improved pain and functional outcomes following THA for patients that can independently mobilise, and have greater than five years life expectancy.^{8,9} These findings have been incorporated into international practice guidelines,¹⁰⁻¹² and consequently, the use of THR for femoral neck fractures in Australia is increasing.^{1,13} Despite improved functional independence and quality of life, the rate of dislocation after THA for hip fracture is more than double that of HA, and approximately

five times higher than the rate after THA for osteoarthritis. Dislocation involves separation of the prosthetic femoral head and acetabular cup and requires closed reduction of the prosthesis under sedation or general anaesthetic to restore a patient's ability to ambulate. For irreducible or recurrent cases, a revision THA may be required. Treatment of recurrent instability is associated with significant costs and decreased patient quality of life.^{14,15} Closed reduction and revision THA incur additional hospital costs of 19% and 148% of an otherwise uncomplicated THA, respectively.¹⁵ Currently, patients undergoing a THR are routinely informed about the risk of dislocation prior to their surgery. Medical and allied health staff often provide "hip precautions" which require patients to restrict their post-operative activity to minimise the risk of dislocation.¹⁶ These restrictions (not flexing beyond 90 degrees, not sitting in deep chairs, not crossing legs) are disruptive to usual activity and are a source of anxiety during recovery as patients are constantly reminded of the risk of dislocation.¹⁷

Dual mobility cup (DMC) has been proposed as an alternative, novel design for THA that is purported to reduce the risk of dislocation in high-risk populations such as femoral neck fractures. The DMC theoretically increases stability by providing an additional articulating surface ('ball-within-ball') compared to traditional THA designs (Figures 1-3).¹⁸ This is achieved by use of a larger head-to-neck ratio and jump distance (i.e. vertical or inferior head displacement required for dislocation) that approximates the size of the natural femoral head (and the size of a hemiarthroplasty) allowing an increased range of motion in all directions before dislocation occurs. In standard THA, impingement of the neck against the polyethylene liner at a single articulation creates a lever effect, increasing the risk of dislocation. In the setting of elective THA performed for osteoarthritis, use of DMC is associated with a significantly decreased risk of dislocation compared to conventional THA in the first post-operative year for both primary and revision THR procedures.¹⁹

[figure not shown]

Figure 1. 'Ball-within-ball' concept of dual mobility THA; 2. Head-to-neck ratio and jump distance, dual mobility versus standard single-bearing total hip arthroplasty; 3. Articular motion of the dual mobility THA, the femoral head rotates within the liner until contact is made at A, at which point the liner then rotates within the acetabular shell B, increasing the range of motion 10-15°.

There is evidence that the use of DMC in the fracture neck of femur population reduces risk of dislocation. A prospective multicentre case series of 214 patients with a mean age of 83 years demonstrated a dislocation rate of 1.4% at 9 months post-operatively.²⁰ A Danish before-and-after case series comparing DMC to bipolar HA in a similar patient demographic reported a slightly higher dislocation rate of 4.6% and 14.6%, respectively. The use of DMC was associated with a significantly

lower incidence of re-operation for dislocation.²¹ A similar before-and-after case series comparing DMC to conventional THA reported dislocations and revision surgery only in the latter group.²² A prospective, randomised feasibility trial in the UK was abandoned due to poor recruitment and results for the sample of 20 patients were not analysed.²³ The most recent systematic review reporting 554 DMC performed for fractured neck of femur found a relatively low dislocation rate of 2.3%.²⁴ Registry data from the Nordic Arthroplasty Register Association (NARA) database demonstrates a greater than 50% reduction in the risk of revision for dislocation using propensity score matching to compare DMC to conventional THA in the fractured neck of femur population.²⁵ Australian registry data, however, does not show a difference in the risk of revision surgery for dislocation, but this may be due to confounding by indication.¹³ For example, DMC may be preferentially used in patients with conditions associated with a higher risk of dislocation such as revision procedures, tumours and hip fractures.

On November 15, 2018, we conducted a focus group with a convenience sample of five patients who had recently had a THA (three for fracture, two elective) at two participating hospitals (St. George and Sutherland). While the main concern patients had during their recovery was the risk of an infection, all patients specifically recalled the risk of dislocation and the recommended precautions, and all reported it as a major source of anxiety. Patients were “particularly careful” and most thought their hip was “going to pop out” if they performed normal activities, such as gardening, cutting their toenails, or driving. Two patients mentioned they were “chastised frequently” by hospital staff for “doing the wrong thing”. Most patients voluntarily opted to use walking aids or held handrails to specifically mitigate dislocation risk and not “upset” the joint. All patients agreed dislocation following hip replacement was an important issue and supported an experimental trial to reduce that risk. The issue of prosthesis novelty was specifically raised, with a single patient expressing concern about having a prosthesis with a shorter track record than “standard” THA. Patients wanted to “move forward with innovations” and did not express concern when asked about consent, with most considering it unnecessary, particularly given that dual mobility THA is approved and is used routinely in many centres (without any specific consent).

Cost-benefit analyses have demonstrated significant savings associated with a reduced incidence of dislocation for primary THA performed for osteoarthritis. Economic modelling of a French cohort assuming a relative risk of dislocation of 0.4 for DMC compared to conventional THA reported 3,283 less dislocations and 882 less revision surgeries at a cost saving of €28.3 million per 100,000 THA procedures.²⁶ Similarly, analysis of direct and indirect costs using administrative and registry databases from the United States demonstrated net cost savings per dislocation saved at a cost difference threshold of \$1,023 (2013 USD) more for DMC implants.²⁷ The DMC design of THA therefore has the potential to reduce the cost burden associated with closed reductions and revision THA performed for instability in a high risk population. A recent editorial from a leading orthopaedic journal called for a high quality, adequately powered trial to determine if routine use of DMC can address the problem of the high rate of dislocation associated with the use of THA in people with fractured neck of femur.²⁸

1.3 Choice of comparators

Both prostheses (DMC and conventional THA) are currently used in usual care for the treatment of femoral neck fractures (FNF). DMC will be labelled the intervention and conventional THA as the comparator.

The trial will allow DMC of any brand. All DMC are similar in design and surgeons / hospitals will be allowed to choose the implant brand of their preference.

Conventional THA will use a polyethylene head size of at least 32 mm unless anatomy does not allow (e.g. unusually small patient).

Each participating surgeon will use the same femoral stem, fixation method and surgical approach for both the intervention (DMC) and control (THA) groups.

1.4 Hypotheses

In patients treated with hip replacement surgery for a recent femoral neck fracture, DMC reduces the risk of dislocation in the first year after surgery compared to conventional THA.

1.5 Primary Aim

To compare the effectiveness of DMC to conventional THA for femoral neck fracture in reducing the risk of hip dislocation in the first post-operative year.

1.6 Secondary Aim

- To compare the revision rates (for dislocation and for any reason) at one, two and five years post-operatively.
- To determine the cost-effectiveness of using DMC compared to conventional THA in reducing the risk of hip dislocation in a hip fracture population.
- To compare the mortality between groups at 30 days, 120 days, and then at one, two and five years post-operatively.

1.7 Primary Outcome Measure

The primary outcome is hip dislocation within one year.

1.8 Secondary Outcomes Measures

1.8.1 Revision surgery for dislocation at 1,2 and 5 years

1.8.2 Revision surgery for any reason at 1, 2 and 5 years

1.8.3 Death at 1, 2 and 5 years

1.8.4 Complications: any unplanned reoperation or readmission related to the surgery within 1 year (see below)

1.8.5 Costs: if DMC is found to be superior to conventional THA, the cost-effectiveness will be analysed (see list below).

Complications will be classified into the following groups:

- Readmission related to the original surgery or associated treatment (yes/no)
- Reason for admission: infection, dislocation, stiffness, fracture, wound dehiscence, implant loosening, migration or failure, wound bleeding, other (non-joint) surgery.
- Reoperation on the same joint (yes/no)
- Reason for reoperation: infection, dislocation, fracture, wound dehiscence, implant loosening, migration or failure.
- Death

2. Methods

2.1 Setting

Eligible hospitals (public and private) performing THA for fractured neck of femur in Australia. The study will be nested within the AOANJRR Clinical Trials Platform, an electronic platform for recruitment and data collection for patients undergoing joint replacement surgery.

2.2 Eligibility

2.2.1 Hospital (Site) Level

- Departmental (or surgeon group) agreement to participate in the study and adhere to study protocols.
- No other changes to practices or protocols relevant to the care of patients with fractured neck of femur over the course of the study.
- All listed investigators will complete Good Clinical Practice (GCP) training prior to commencement of the study if not completed within the past three years.

2.2.2 Patient Level

2.2.2.1 Inclusion Criteria

1. Displaced femoral neck fracture suitable for standard THA (e.g. no pre-existing deformity requiring custom or non-standard prostheses)
2. Aged 50 years or older
3. Patient meets Australia New Zealand Hip Fracture Guidelines¹⁰ for management of a displaced intracapsular hip fracture with a total hip replacement:
4. Able to walk independently out of doors with no more than use of a stick prior to the fracture
5. Not cognitively impaired
6. Medically fit for anaesthesia and the procedure

2.2.2.2 Exclusion Criteria

- For the primary analysis, the following exclusions will apply at a patient level:
- Dementia or other significant cognitive impairment
- Resident of a permanent residential aged care facility
- Pathological fracture due to tumour

2.3 Sample Size

A recent large randomised controlled trial of 1495 patients from 80 institutions in 10 countries demonstrated a 4.7% incidence of dislocation in the two years following THA for fractured neck of femur in patients aged greater than 50 years.²⁹ This compared to a 2.7% dislocation incidence for patients that received hemiarthroplasty in the same study. A systematic review and meta-analysis of randomised controlled trials comparing hemiarthroplasty to THA that included outcomes from five studies reported a 3.3% incidence of dislocation for hemiarthroplasty and 8.5% for THA.⁹ The cumulative percent revision of primary conventional total hip replacement performed for fractured neck of femur in Australia is 3.0%, 5.3% and 7.9% at 1, 5 and 10 years respectively, of which prosthesis dislocation (32.5%) is the most common indication.¹³

For the sample size for the DISTINCT study, we anticipate an overall dislocation rate of 4-5% at one year based on the above data. A recent systematic review of DMC performed for FNF reported an incidence of dislocation of 2.5% and an overall revision of 2.3% at a mean follow-up of 1.3 years.²⁴ A matched-pair analysis from the Nordic Arthroplasty Registry Association (NARA) reported approximately half the revision rate for dislocation for DMC compared to conventional THA.²⁵ With targets of 6% and 3% for conventional THR and DMC, respectively (halving the revision rate as previously reported using Nordic registry data²⁵), a cluster-randomised trial using at least 48 clusters would require 16 patients per

group, per cluster ($n = 1,536$) with 80% power and a significance level of 5% ($ICC = 0.01$, $IPC = 0.008$). As the outcome is cumulative incidence (regardless of mortality) and achieved through data linkage, no adjustment for death or loss to follow up has been made. The study will recruit a minimum of 16 patients per group (32 total) per cluster. This sample size would provide 90% power for a higher event rate of 8% and 4% for the two groups.

2.4 Recruitment

Hospitals will be approached individually by the lead CI and the study team, based on high usage of THA for hip fractures. A site will be considered eligible if they perform 15 THA for hip fracture within 12 months, allowing recruitment with 24 months. Departmental (or surgeon group) agreement with the study protocol and the individual treatment protocols (for each group) will be required. Sites where a subgroup of attending surgeons agree to participate will be included if the number of eligible patients for that group of surgeons per year is at least 15. A site investigator will be nominated for each site.

2.5 Blinding

Sites will not be blinded to group allocation. Patients will be informed of a study comparing two different but common types of THA used for fractured neck of femur

The statistical analysis will be blinded. The Writing Committee will be blinded and will prepare two separate manuscripts based on the possible group allocations.

2.6 Randomisation

Each site will be randomised with a 1:1 allocation with a computer-generated random sequence. Simple randomisation will be used (no use of blocks, no stratification). The allocation will refer to the first intervention.

2.7 Intervention

Each site will be allocated to two consecutive periods of standard protocol of DMC and standard protocol of conventional THA for management of FNF in eligible patients with the order of the two periods determined by randomisation at a 1:1 ratio on an open label basis. Allocation will occur one month (3 – 6 weeks) prior to site commencement to allow introduction of local protocols and supply of implants.

Each site will adhere to the initially randomised protocol for a time period based on surgical volume aiming for 16 patients eligible for the primary analysis per group (32 total per site).

Patients will be informed of the trial during initial data entry. Patients will be specifically asked at the time of study for consent to follow up, for use of their data in research, and use of linked data to measure and verify surgical outcomes. Patients will not be individually consenting to be randomised to either DMC or conventional THA, as both surgical implants represent standard practice and randomisation is not at the patient level. Further details on the consent process is listed in the protocol (section 4.3).

Patients will be followed by the AOANJRR by recording and matching revision procedures and mortality, as per usual practice. There will be no change to usual medical follow up (clinic attendance, investigations etc.). The outcome (dislocation) will be determined by data linkage between the AOANJRR and hospital level data acquired through state governments or the Australian Institute for Health and Welfare.

Total hip arthroplasty using both conventional and dual mobility design will be performed as per standard surgical technique according to surgeon preference, using the same surgical approach for

both treatment groups. Patients who have a contraindication to either implant design will be treated as per local protocols.

2.8 Adherence

Adherence to study protocol will be determined using standard AOANJRR data (prosthesis details)

2.9 Concomitant Care

Standardisation of surgery and post-operative treatment will be required as follows:

- Surgical approach can vary by surgeon, but individual surgeons must maintain the same approach criteria for both study groups
- If a posterior approach is used, a capsule repair will be performed
- Weight bearing without restriction post-operatively
- Splinting will not be used routinely
- Education and information around hip precautions will be consistent across groups
- Each site will provide the same rehabilitation approach for both treatment arms

2.10 Additional Care

As both interventions are standard, recommended practice, no additional treatment will be provided for participants.

2.11 Data Collection/Schedule

Data collection for baseline data and follow-up at 1 year, 2 years and 5 years will be via standard (currently routine) forms submitted to the AOANJRR for revision total hip arthroplasty and through data linkage.

| Time Point | Data Collection Questions and Instruments |
|------------------|---|
| Pre-operative | Age Sex Joint (hip) Side Unilateral vs bilateral Primary or revision ASA grade BMI |
| 1 year | Dislocation (via linked data) Revision surgery (via AOANJRR) Complications (via linked data) |
| 2 years, 5 years | Revision surgery (via AOANJRR) Death (via linked data) |

The AOANJRR already collects data on almost all joint replacement procedures performed in Australia. The operative data are completed at the time of surgery on a Registry form. These forms are collated each month by the hospital and sent to the Registry for data entry into the secure Registry database. This process will remain unchanged.

The Registry currently stores identified patient data for several reasons;

1. Procedures for the same patient need to be linked together in the Registry using patient identifiers to track the joint history.
2. The Registry links to the NDI twice a year in order to flag if a patient has died.

Furthermore, identified information is required for this registry-nested study because the Registry data needs to be linked to hospital level data acquired through state governments or the Australian Institute for Health and Welfare using patient identifiers.

2.12 Data Monitoring and Cleaning

A separate Data Quality Committee will be established to monitor data management and quality. A separate safety monitoring committee will not be established, and no stopping rules will be used as both interventions are commonly used and recommended treatments. No interim analysis will be performed; this will reduce the chance of early stopping due to spurious findings. Adverse events (separate to complications listed under secondary outcomes) will be monitored by the Trial Management Committee.

2.13 Auditing and Data Validation

Revision surgeries recorded by the AOANJRR are validated by cross-referencing with hospital-level data and unmatched revisions are verified by contacting individual sites.

The AOANJRR Data Linkage project will be used to measure readmission and reoperation. The AOANJRR also links to the National Death Index (NDI) twice per year (February and September) to measure mortality.

2.14 Statistical analysis

The analysis for the primary aim will test between-group difference in the proportion of cases sustaining a dislocation of the affected hip within one year post-operatively. The primary analysis will use cluster summary methods. These methods estimate the treatment effect using cluster level differences and have been shown to be appropriate for cluster randomised crossover trials with rare outcomes and the intracluster and interperiod correlation coefficients expected in this trial. Multiple imputation will be used to account for missing outcome data, using auxiliary variables gathered from routine AOANJRR data (including age, sex, baseline health, pain and function, diagnosis and surgical factors).

Secondary analyses will be performed for the primary outcome, to test for differences in treatment effect between subgroups of patients: surgical approach, ASA grade, BMI grade and gender. The analysis method will be the same as the primary outcome and will include an interaction term between subgroup and treatment group.

Secondary analyses will include an analysis of all-cause revision, revision for dislocation, and other complications (death, re-operation and readmission rates). Cluster summary methods will be used for all secondary analyses.

If DMC are found to be superior to conventional THA, a cost effectiveness analysis of DMC compared to conventional THA will be performed from a health system perspective, calculating the cost per dislocation saved. The only difference in input costs will be the difference in implant costs, as all other care costs will be equal.

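### Sites know the period's implant before judging who is suitable for THA, and the primary analysis in 2.14 gives measured case mix no stated role

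*Protocol*

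**What the plan says.** **Allocation is open and known early.** Protocol 2.5 states "Sites will not be blinded to group allocation". Section 2.7 puts allocation three to six weeks before a site starts, so every patient is identified after it.

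**Entry involves judgement.** The first inclusion criterion in 2.2.2.1 is "Displaced femoral neck fracture suitable for standard THA", and another is medical fitness for the procedure. The criteria are tied to a named guideline and are the same in both periods.

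**There is an alternative operation.** Section 1.2 describes hemiarthroplasty (HA) as the traditional treatment and says that "the rate of dislocation after THA for hip fracture is more than double that of HA".

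**Primary analysis.** Section 2.14 says "The primary analysis will use cluster summary methods" and explains that the effect is estimated from cluster-level differences. Covariates are mentioned as auxiliaries for imputing missing outcomes, and surgical approach, ASA grade, BMI grade and gender as subgroup factors.

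**Baseline data.** The pre-operative row of the table in 2.11 reads "Age Sex Joint (hip) Side Unilateral vs bilateral Primary or revision ASA grade BMI".

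The protocol describes no screening log and no count of eligible patients who were given hemiarthroplasty. Section 2.8 checks adherence from prosthesis details.

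**The concern.** In a cluster-crossover trial with open allocation, randomisation protects the order of the periods. It does not protect the choice of which patients enter each period. A surgeon who thinks a patient prone to dislocate might lean towards hemiarthroplasty in the conventional period and accept the same patient for THA in the DMC period. The DMC periods would then hold a higher-risk group. The reverse is also possible, for example if surgeons were more cautious with the less familiar implant.

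Either way, the difference between a site's two periods would mix the implant effect with a difference in who was treated. The design has 80% power at its target, so a modest dilution costs power. With no true effect, the same mechanism could produce an apparent one.

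**Working it through.** **1. The plan's own figure.** Inputs from 2.3: "With targets of 6% and 3% for conventional THR and DMC, respectively"; at least 48 clusters with 16 patients per group per cluster; ICC 0.01; interperiod correlation (IPC) 0.008; 80% power; 5% significance (two-sided assumed).

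- Individually randomised size for 6% v 3%, without continuity correction: 749 per group.
- Design effect: 1 + (16 − 1) × 0.01 − 16 × 0.008 = 1.022.
- 749 × 1.022 = 765.5 per group; 765.5 / 16 = 47.8, rounded up to 48 clusters; 48 × 2 × 16 = 1,536.
- Power at 768 / 1.022 = 751 effective patients per group: 80.2%. At 8% v 4%: 90.5%.

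The stated sample size and both power statements reproduce. There is no arithmetic error here.

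**2. Which case-mix differences matter.**

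- Stable differences between sites cancel in the within-site comparison.
- Secular shifts balance in expectation, because period order is randomised (2.6, 2.7).
- Random variation between periods is allowed for by setting the IPC (0.008) below the ICC (0.01).
- Selection that depends on the period's implant follows the treatment label at every site. None of these features removes it.

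**3. Illustration A: extra high-risk cases in DMC periods.** The shares and relative risks are assumed; the protocol gives none. If a share x of DMC-period patients are extra cases at r times the risk, the DMC rate is 0.03 × (1 − x + x·r), and the difference is taken from 6%.

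| x | r | DMC rate | Difference (points) | Power |
|---|---|---|---|---|
| 0 | – | 3.0% | 3.0 | 80% |
| 0.1 | 2 | 3.3% | 2.7 | 70% |
| 0.1 | 3 | 3.6% | 2.4 | 59% |
| 0.2 | 3 | 4.2% | 1.8 | 35% |

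**4. Illustration B: a high-risk stratum present in both periods.** Assumed: the stratum is a share b = 20–30% of conventional-period patients, has relative risk r = 1.5–3, and its share is s = 5–20 points higher in DMC periods. The conventional rate is held at 6%. The low-risk rate is 0.06 / (1 − b + b·r). With no true effect, the DMC-period rate is that rate × (1 − (b + s) + (b + s)·r). A true halving multiplies it by 0.5.

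- Mild (b = 0.3, r = 1.5, s = 0.05): low-risk rate 5.22%. The DMC-period rate with no effect is 6.13%, a bias of 0.13 points. With a true halving the difference is 6 − 3.07 = 2.93 points and power is 78%.
- Middle (b = 0.2, r = 2, s = 0.10): low-risk rate 5.0%; 6.5% with no effect, a bias of 0.5 points. With halving, 2.75 points and 72% power.
- Strong (b = 0.2, r = 3, s = 0.20): low-risk rate 4.29%; 7.71% with no effect, a bias of 1.71 points. With halving, 2.14 points and 48% power.

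With no true effect, the chance of rejecting at nominal 5% runs from 5.1% to 26% over this grid.

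**5. Opposite direction.** Take the middle case with the stratum share 10 points lower in DMC periods. The DMC-period rate with no effect is 0.05 × (1 − 0.1 + 0.1 × 2) = 5.5%, a spurious 0.5 points in favour of DMC. With a true halving the difference is 6 − 2.75 = 3.25 points.

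**The case against.** **Section 2.14 does not say the analysis is unadjusted.** A reader might infer this from the reference to cluster-level differences, but the text does not support it. A cluster summary method can be covariate-adjusted, and the detail may be in a SAP that is not shown. This stands: 2.14 contains no error or contradiction. What remains is that it gives the collected covariates two roles, and adjustment is not one of them.

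**Not every case-mix shift biases the effect.** This stands, for the reasons in step 2 of the working.

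**The protocol does not itself name this mechanism.** Section 1.2 says "DMC may be preferentially used in patients with conditions associated with a higher risk of dislocation", and a reader might take that as an acknowledgement. The sentence goes on to give revision procedures, tumours and hip fractures as its examples. It concerns choice of implant across indications in registry data, not choice between hemiarthroplasty and THA among hip-fracture patients. All trial patients have a displaced femoral neck fracture, and pathological tumour fractures are excluded from the primary analysis. It should not be cited for this point.

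**There are safeguards.** Section 2.2.1 requires agreement to follow the protocol and no other relevant practice changes. Section 2.2.2.1 applies guideline criteria in both periods, and 2.2.2.2 excludes cognitive impairment and permanent residential care. These limit implant-dependent selection. They leave room for judgement on suitability and fitness, and no record is described that would show whether that judgement differed between periods.

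**Adjustment reaches the mechanism only in part.** A surgeon's impression of dislocation risk is only partly captured by age, sex, ASA grade and BMI. This stands, and is why the tabulation is needed as well.

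**Conclusion.** The point holds as a limited one. Open allocation, known before patients are judged suitable for THA and with hemiarthroplasty available, leaves the within-site difference open to implant-dependent selection. Randomised order and within-site comparison do not correct it. Section 2.14 does not exclude adjustment but gives measured case mix no stated role in the primary comparison.

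The size is illustrative only. Under the assumed shares and relative risks, with selection against DMC, the planned difference falls from 3.0 to between about 1.8 and 2.9 points. That is negligible for a small shift in a weak risk factor and material for a large shift in a strong one. The protocol supplies neither the shares nor the risks.

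A reader might also infer that the bias must run against DMC and hide a true benefit. The protocol does not establish a direction, and the opposite shift would favour DMC. It does not show that such selection occurs. The case for acting is that the correction is cheap and would make differential selection visible if it happens.

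**What to change.** **In 2.14, pre-specify a two-stage covariate-adjusted cluster-summary analysis:**

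1. Model dislocation on age, sex, ASA grade, BMI and period, without treatment.
2. Form observed-minus-expected residuals for each site-period.
3. Analyse the within-site differences in those residuals.

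Report the result alongside the unadjusted difference, and state in advance which of the two is primary. If the SAP already contains this, a cross-reference from 2.14 is enough.

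**Add a descriptive table** of THA numbers and baseline case mix by site and period, with hemiarthroplasty counts for femoral neck fracture where registry data allow. Whether the registry holds those counts in usable form should be confirmed first.

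**Cost.** Wording and analysis time; recruitment, treatment and sample size do not change. The covariates are already in the 2.11 table. A rule for missing BMI or ASA grade is needed. The covariate list should stay short: the planning rates imply about 768 × 0.06 + 768 × 0.03 = 46 + 23 = 69 dislocations. Adjustment will not correct for unmeasured reasons for selection, and the report should say so.
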